1.3.4. Procedures for Adult Participants With (Suspected) COVID-19

Procedures	Study Period				
	COVID-19 Day 1-2	COVID-19 Day 3-5 ^b		7-day cycle to be repeated ^{c,d,e,f}	COVID-19 Day 29 (±7 d) ^{g,h}
Timing relative to onset of signs and symptoms		Part 1	Part 2 ^c		
Location	Home ⁱ	Site ^j	Site ^{j,k}	Site or Home ^k	Site or Home ^{j,k}
Participant to contact study site with any health concerns/participant notifies the site of becoming aware of a positive RT PCR test	●				
Site to contact participant if COVID 19 signs or symptoms are recorded in eCOA	●				
Confirmation of suspected COVID 19 using prespecified criteria	● ^l	● ^m			
Nasal swab sample (collected by the participant at home) ⁿ	● ^o			●	
Nasal swab sample (collected by qualified study staff)		● ^p			
Humoral immunity (serum)			● 10 mL		● 10 mL, ^q
Biomarker blood sample (PAXgene [®] tubes, whole blood)			● 2.5 mL		● 2.5 mL
In case of signs and symptoms: Symptoms of Infection with Coronavirus 19 (SIC), including highest body temperature over the last 24 hours measured by the participant (ePROs to be completed by the participant in the eCOA) ^f		Daily			● ^s
In case of no signs or symptoms: (Suspected) COVID 19 surveillance (symptom check)		At least twice a week			●
Vital signs ^t		●			●
Targeted physical examination		●			●
Pulse oximetry by site staff		●			●
In case of signs and symptoms: Pulse oximetry by the participant (ePRO) to be completed by the participant in the eCOA) ^u	● ^o	3 times a day			
Medical history (including recent flu or pneumococcal vaccination) and description of COVID 19 episode (collected by interview with the participant)			●		●
Concomitant therapies associated with COVID 19		Continuous			
Study site personnel to contact participant		At least weekly			

- a. Note: “Participant” refers to adult participants, either pregnant or postpartum
- b. The visit at COVID 19 Day 3 5 should be scheduled 2 to 4 days after symptoms onset/positive RT PCR test from outside the study.
- c. Only applicable for participants that meet the prespecified criteria for suspected COVID 19 (see Section 8.1.2.4) on COVID 19 Day 1 2 and COVID 19 Day 3 5.
- d. Participant should be encouraged by the site to have nasal swabs collected as indicated in the Schedule of Activities. If the participant is unable or unwilling to have all samples collected as requested, the participant should still complete the other COVID 19 assessments, including the visit at COVID 19 Day 29.
- e. If the nasal swabs collected on COVID 19 Day 1 2 and COVID 19 Day 3 5 are negative for SARS CoV 2, the participant will not undertake any further COVID 19 procedures and will fall back to the default Schedule of Activities in Section 1.3.1 or Section 1.3.2 until the end of the study/early withdrawal.

- f. Participants should undertake the COVID 19 procedures until 14 days after symptom onset (COVID 19 Day 15) or until resolution of the COVID 19 episode, whichever comes last. Resolution of a COVID 19 episode is defined as having 2 consecutive SARS CoV 2 negative nasal swabs and 2 consecutive days with no COVID 19 related signs or symptoms. Once past COVID 19 Day 15, participants should stop the collection of nasal swabs samples as soon as 2 consecutive nasal samples are SARS CoV 2 negative, but (if still symptomatic at that time) should continue completing the ePROs (including SIC, body temperature, and pulse oximetry) in the eCOA until 2 consecutive days with no COVID 19 related signs or symptoms.
- g. Only applicable for participants that have at least 1 SARS CoV 2 positive nasal swab collected on COVID 19 Day 1 2 or Day 3 5. COVID 19 Day 29 should still be performed even if the nasal swab results are still pending.
- h. The visit on COVID 19 Day 29 can be combined with a regular study visit if within the applicable visit windows.
- i. The COVID 19 Day 1 2 nasal swab can be collected at the study site (or hospital or other location, if needed), if preferred by the participant.
- j. All COVID 19 Day 3 5 and Day 29 assessments may be performed by a trained HCP at the participant's home, if allowed per local regulations.
- k. If a participant has a positive test result for SARS CoV 2 infection and/or depending on the medical status of the participant. If necessary, study site personnel or a trained HCP may visit the participant at home (or at the hospital or other location, if needed), if allowed by local regulations. Under these circumstances, the participant will be contacted by the site at least once per week.
- l. In case of COVID 19 like symptoms, based on the information collected through the SIC, the site will reach out to the participant at the latest on COVID 19 Day 2 (the day after the day of symptom onset) to assess whether the reported signs and symptoms qualify as a suspected COVID 19 episode using prespecified criteria (Section 8.1.2.4). As several of the prespecified criteria for suspected COVID 19 overlap with vaccine related reactogenicity, investigators' clinical judgement is required to exclude vaccine related events when assessing suspected COVID 19. In case the participant would actively reach out to the site already on COVID 19 Day 1, the site should already make a first assessment on COVID 19 Day 1 to check whether the reported signs and symptoms qualify as a suspected COVID 19 episode using prespecified criteria (Section 8.1.2.4).
- m. In case of COVID 19 like symptoms, the site will interview the participant to assess whether the reported signs and symptoms still qualify as a suspected COVID 19 episode using prespecified criteria (Section 8.1.2.4).
- n. A nasal swab should be collected from the participant at home (using available material for home swabs provided by the study staff) as soon as the prespecified criteria for suspected COVID 19 are met and preferably on the day of symptom onset or the day thereafter (COVID 19 Day 1 2). The sample collected on COVID 19 Day 1 2 should be transferred to the study site, as arranged by the study site, as soon as possible after collection, preferably within 3 days. Nasal swabs should also be collected once every 7 days until 14 days after symptoms onset (COVID 19 Day 15) or until resolution of the COVID 19 episode, whichever comes last. These samples should be transferred to the study site, as arranged by the study site, within 3 days after collection. Details are provided in the laboratory manual. If the participant requires assistance, a trained HCP can help the participant to collect the nasal swabs. If 2 consecutive nasal swabs negative for SARS CoV 2 are not available due to operational reasons (eg, delays in results availability), participants may cease collection of nasal swabs at the COVID 19 Day 29 visit, provided they have 2 consecutive days with no COVID 19 related signs and symptoms. In these cases, participants may be asked to resume sample collection if nasal sample results once available do not present with 2 consecutive negative swabs for SARS CoV 2. All nasal swabs will be tested by a local laboratory for case management.
- o. The nasal swab should be collected and pulse oximetry (3 times a day), should be started as soon as possible after it has been confirmed that the prespecified criteria for suspected COVID 19 (Section 8.1.2.4) are met. On the first day the participant experiences signs/symptoms, the participant should record at least 1 of the 3 pulse oximetry readings in the last 24 hours in the eCOA.
- p. Nasal swabs will be tested by a local laboratory for case management. For participants with suspected COVID 19, confirmation of SARS CoV 2 infection by RT PCR or other molecular diagnostic test at a central laboratory may be used for the analysis of the case definition.
- q. Blood sample for humoral immunity may include a sample for sero confirmation of previous SARS CoV 2 infection (antibody).
- r. Participants should complete the (suspected) COVID 19 surveillance (symptom check) in the eCOA. In case of COVID 19 like signs and symptoms, participants should be encouraged by the site to complete the SIC daily, preferably in the evening around the same time each day, starting on the first day they experience symptoms. Sites should remind the participant to complete the SIC, unless special circumstances occur such as hospitalization or ventilation, in which case the reason for not completing the SIC should be recorded by site staff in the clinical database. If signs and symptoms are still ongoing on COVID 19 Day 3 5, collection of SIC will be continued until at least 14 days after symptoms onset unless both COVID 19 Day 1 2 and COVID 19 Day 3 5 nasal swabs are negative. If either of the swabs are positive or the result is unknown AND the participant is beyond 14 days after onset of symptoms, the SIC can be stopped after 2 days without signs and symptoms.
If a participant is unable to complete the eCOA, a study staff member or a caregiver can collect information on the participant's behalf as detailed in Section 8.1.2.1.
Participant should measure body temperature daily (oral route preferred, or in accordance with the local standard of care) and record the highest temperature in the last 24 hours.
- s. If the participant does not have symptoms at that time, he/she will only need to complete the (suspected) COVID 19 surveillance (symptom check) in the eCOA.

- t. Includes measurement of vital signs (preferably supine systolic and diastolic blood pressure, heart rate, and respiratory rate [after at least 5 minutes rest] and body temperature). It is recommended that vital signs are measured before collection of nasal swabs and blood draws.
- u. In case of COVID 19 like symptoms, the participant will be asked to measure blood oxygen saturation and pulse rate at home 3 times a day (preferably in the morning, at lunch time, and in the evening). The results will be recorded by the participant in the eCOA.

Upon closure of the COVID 19 episode and procedures, all participants will fall back to the default Schedule of Activities. Closure of a COVID 19 episode should occur at the last study visit. If the episode is ongoing, it should be marked as such in the eCRF. The episode will be followed by the investigator until resolution or until a clinically stable condition is reached, and the outcome recorded in the participant's medical chart.

COVID 19 coronavirus disease 2019; eCOA electronic clinical outcome assessment; RNA ribonucleic acid; SARS CoV 2 severe acute respiratory syndrome coronavirus 2; SIC Symptoms of Infection with Coronavirus 19.

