The adult participant will be asked to continue to complete the ePROs in the eCOA as specified above for COVID-19 Day 1:

- SIC (including body temperature): every day, preferably in the evening around the same time each day. If more than one measurement is made on any given day, the highest temperature of that day will be recorded.

- Blood oxygen saturation and pulse rate using a pulse oximeter 3 times a day, preferably in the morning, at lunch time, and in the evening.

Note: the ePROs do not have to be completed if special circumstances occur, such as hospitalization or ventilation, in which case the reason for not completing the ePROs should be recorded by site staff in the eCRF.

The adult participant will be asked to collect a nasal swab at home on **COVID-19 Day 1-2**, as soon as possible after it has been confirmed that the prespecified criteria for suspected COVID-19 are met. If the adult participant requires assistance, a trained HCP can help the participant to collect the nasal swab. The study site should arrange transfer of the nasal swab to the study site as soon as possible after collection, preferably within 3 days. The COVID-19 Day 1-2 nasal swab can also be collected at the study site (or hospital or other location, if needed), if preferred by the adult participant.

Day 1-2 Procedures in Case of a Positive RT-PCR Test Outside the Study Site Context

If an adult participant becomes aware of a positive RT-PCR test for SARS-CoV-2 she should contact the site as soon as possible. The day the adult participant became aware of the positive PCR test will be considered **COVID-19 Day 1**. Regardless of whether the adult participant is symptomatic or asymptomatic, they will be asked to:

Complete the (suspected) COVID-19 surveillance (symptom check) in the eCOA. In case of COVID-19-like signs and symptoms they will need to complete the SIC (including body temperature) in the eCOA.

The adult participant will be asked to collect a nasal swab at home on **COVID-19 Day 1-2**, as described for the participants with signs and symptoms (see above).

If a participant has a positive test result for SARS-CoV-2 infection, if necessary, study-site personnel may visit the participant at home^a. The participant will be contacted by the site at least once per week. The SIC will be reviewed by study staff during these contacts (phone call or visit).

Day 3-5 Procedures for all Adult Participants Who Have met the Prespecified Criteria for (Suspected) COVID-19

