The adult participant will be asked to come to the site on **COVID-19 Day 3-5** (between 2 and 4 days after symptom onset/becoming aware of a positive RT-PCR test).

If a site visit is not feasible, a member of the study staff could visit the participant at home (or at the hospital or other location, if needed), if allowed by local regulations. The study staff visiting participants at home will use personal protective equipment according to local regulations. The COVID-19 Day 3-5 assessments may also be performed by a trained HCP, if allowed per local regulations.

During **Part 1** of the **COVID-19 Day 3-5** visit, if the adult participant has experienced COVID-19 like signs and symptoms, the site will interview the participant to assess whether the reported signs and symptoms still qualify as a suspected COVID-19 episode

^a The study staff visiting participants at home will use personal protective equipment according to local regulations.

using prespecified criteria (Section 8.1.2.4). In addition, for all participants with (suspected) COVID-19, a qualified member of the study site will measure vital signs (body temperature, blood pressure, heart rate, and respiratory rate) and pulse oximetry. A targeted physical examination will be performed based on the judgement of the investigator or designated medically qualified healthcare professional. A nasal swab will be collected for detection of SARS-CoV-2 by a qualified member of the study site.

If the prespecified criteria for suspected COVID-19 are still met on COVID-19 Day 3-5 or if at least one nasal swab from COVID-19 Day 1-2 or Day 3-5 visits is positive for SARS-CoV-2 (tested by RT-PCR), the following assessments and procedures are to be performed during **Part 2** of the **COVID-19 Day 3-5** visit: blood samples for exploration of biomarkers that correlate with SARS-CoV-2 infection and COVID-19 severity and for exploration of antibody responses to infection with SARS-CoV-2 will be collected by a qualified member of the study site and the procedures for the 7-day cycles should be started (see below).

The medical history (general and obstetric) and description of COVID-19 episode will be collected by interview with the participant.

If signs and symptoms are still ongoing on COVID-19 Day 3-5, collection of SIC will continue as specified in the next section ([Closure of the COVID-19 episode](#)).

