If the prespecified criteria for suspected COVID-19 are no longer met on COVID-19 Day 3-5, the participant will not undertake any further COVID-19 procedures. She will fall back to the default Schedule of Activities.

Procedures During the 7-day Cycles

If an adult participant meets the prespecified criteria at Day 3-5 (even if nasal swab results from Day 1-2 and Day 3-5 are pending) and/or has at least one positive nasal sample for SARS-CoV-2 at COVID-19 Day 1-2 or COVID-19 Day 3-5, she will be asked to undertake the COVID-19 procedures, in particular:

In case of signs and symptoms: The participant will be reminded to further complete the ePROs in the eCOA as described for COVID-19 Day 1-2:

In case the nasal swabs collected at Day 1-2 or Day 3-5 visits are tested positive for SARS-CoV-2 and the participant is asymptomatic: The participant will be reminded to further complete (suspected) COVID-19 surveillance (symptom check, at least twice a week).

All participants will be asked to collect a nasal swab at home once every 7 days. If the participant requires assistance, a trained HCP can help the participant to collect the nasal swabs. The study site should arrange transfer of the nasal swabs to the study site within 3 days after collection. Details are provided in the laboratory manual.

If, due to lack of signs and symptoms and unavailability of results from nasal swabs collected on Day 1-2 and/or Day 3-5 visits, the participant stopped the COVID-19 procedures and returned to default Schedule of Activities on COVID-19 Day 3-5, the

participant will be contacted as soon as at least one of these samples is found to be positive for SARS-CoV-2. The participant will be asked to resume COVID-19 procedures until 14 days after symptom onset (COVID-19 Day 15) or until resolution of the COVID-19 episode, whichever comes last.

Note: If results of both Day 1-2 and Day 3-5 nasal swabs once available are negative, the participant will stop the 7-day cycle and fall back to the default [Schedule of Activities](#).

Note: Participants should be encouraged by the site to collect nasal swabs as indicated in Section 1.3.4. If the participant is unable or unwilling to collect all samples as requested, the participant should still complete the other COVID-19 assessments, including the visit at COVID-19 Day 29.

COVID-19 Day 29 Procedures

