resolution of the COVID-19 episode, whichever comes last^a. Resolution of the COVID-19 episode is defined as having 2 consecutive SARS-CoV-2 negative nasal swabs and 2 consecutive days with no COVID-19-related signs or symptoms. Once past COVID-19 Day 15, participants should stop the collection of nasal swabs as soon as 2 consecutive nasal swabs are SARS-CoV-2 negative, but (if still symptomatic at that time) should continue completing the ePROs (including SIC, body temperature, and pulse oximetry) in the eCOA until 2 consecutive days with no COVID-19-related signs or symptoms.

If signs and symptoms are still ongoing on COVID-19 Day 3-5, collection of SIC will be continued until at least 14 days after onset unless both COVID-19 Day 1-2 and COVID-19 Day 3-5 nasal swabs are negative. If either of the swabs is positive or the result is unknown AND the participant is beyond 14 days after onset of symptoms, the SIC can be stopped after 2 days without signs and symptoms.

For participants with a positive test result for SARS-CoV-2 infection, a study visit will be conducted 28 days after symptom onset (ie, at the COVID-19 Day 29 visit) to assess the clinical course of the infection.

If 2 consecutive nasal swabs negative for SARS-CoV-2 are not available due to operational reasons (eg, delays in results availability), participants may cease collection of nasal swabs samples at the COVID-19 Day 29 visit, provided they have 2 consecutive days with no COVID-19-related signs and symptoms. In these cases, participants may be asked to resume sample collection if nasal sample results once available do not present with 2 consecutive negative swabs for SARS-CoV-2.

Upon closure of the COVID-19 episode and procedures, all adult participants will fall back to the default Schedule of Activities^b (Section 1.3.2).

If the adult participant experiences new signs or symptoms suggesting possible COVID-19 at a later point in time, the participant would restart the COVID-19 procedures from COVID-19 Day 1 onwards.

8.1.2.2. Procedures for Neonate and Infant Participants in Case of Signs and Symptoms of COVID-19

The following procedures are specific for the study:

Day 1-3 Procedures in Case of Signs and Symptoms

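### The adult COVID-19 schedule and Section 8.1.2.1 disagree on whether a woman positive on a study swab but symptom-free by Day 3-5 continues, so some exploratory samples may be selected on symptom duration

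*Protocol*

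**What the plan says.** Two places make continuation depend on the criteria for suspected COVID-19 alone.

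- Section 1.3.4, footnote c, attached to Part 2 of the Day 3-5 visit and to the 7-day cycle: "Only applicable for participants that meet the prespecified criteria for suspected COVID 19 (see Section 8.1.2.4"), on Day 1-2 and also on Day 3-5.
- Section 8.1.2.1, end of the Day 3-5 procedures: "If the prespecified criteria for suspected COVID-19 are no longer met on COVID-19 Day 3-5, the participant will not undertake any further COVID-19 procedures".

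Three places in Section 8.1.2.1 let a positive study swab suffice.

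- Part 2 is opened if the criteria are "still met on COVID-19 Day 3-5 or if at least one nasal swab from COVID-19 Day 1-2 or Day 3-5 visits is positive".
- The 7-day cycle is opened if she meets the criteria on Day 3-5 "and/or has at least one positive nasal sample for SARS-CoV-2".
- The closure rule ends the episode early only when both swabs are negative. It continues the procedures when either is positive.

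Day 1 also has more than one anchor. Section 8.1.2.1 describes it as the day of onset for a symptomatic woman. For a PCR test outside the study it says: "The day the adult participant became aware of the positive PCR test will be considered" Day 1. Footnote b of Section 1.3.4 counts the Day 3-5 visit from symptom onset or from the outside test itself. Day 15 is tied to symptom onset, and for the last visit the text is: "a study visit will be conducted 28 days after symptom onset (ie, at the COVID-19 Day 29 visit").

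**The concern.** A site cannot obey all of these rules for a woman who tested positive on a study swab and has recovered by the Day 3-5 visit. Under one set she gives serum and PAXgene and enters the weekly swab cycle; under the other she returns to the default schedule.

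The Part 2 blood is meant for biomarkers of infection and of COVID-19 severity, and for the antibody response to infection. If that sample exists only for women whose symptoms persist, its availability depends on something close to the severity being studied. A correlation with severity would then be estimated in a group from which the shortest illnesses have been removed.

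The Day 1 wording is a lesser matter of the same kind: one visit label may cover different times since onset, depending on how the episode was found.

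**Working it through.** **Who is in conflict.** The criteria in Section 8.1.2.4 list a positive RT-PCR from a laboratory independent of the study, with or without symptoms. They do not list a positive study swab. On the literal text:

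- outside PCR positive, symptoms gone: criteria still met, so footnote c lets her continue;
- study swab positive, symptoms persisting: criteria met, no conflict;
- both study swabs negative: footnote e and the closure rule both stop, no conflict;
- study swab positive, no outside positive PCR, symptoms gone by Day 3-5: conflict.

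**What each rule does for that last woman.**

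| Rule | Part 2 blood | 7-day swabs | Day 29 blood |
|---|---|---|---|
| 1.3.4 footnote c | no | no | not addressed |
| 8.1.2.1 stop sentence | no | no | no, if literal |
| 8.1.2.1 Part 2 gate | yes | yes | not addressed |
| 8.1.2.1 7-day-cycle gate | not addressed | yes | not addressed |
| 8.1.2.1 closure rule | procedures continue | procedures continue | yes, if positive |
| 8.1.2.1 recall clause | too late for Day 3-5 | resumed | not addressed |
| 1.3.4 footnote g | not addressed | not addressed | yes |

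The recall clause covers a woman who stopped without symptoms while results were pending. She is contacted once a swab proves positive and resumes procedures.

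**What lies outside the gate.** The Day 1-2 swab and the Part 1 swab of the Day 3-5 visit are taken before it. Day 29 blood depends on a positive swab (footnote g).

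**Size of the selection.** Let s be the share of study-swab-positive women, without an outside positive PCR, who are symptom-free by Day 3-5. The protocol gives no value, so s is an assumption.

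- Footnote c: Part 2 sampled in 1 − s, which is 90%, 80%, 70% and 50% for s = 10%, 20%, 30% and 50%.
- Part 2 gate of Section 8.1.2.1, all results known at the visit: 100%.
- The same gate with a share q of results known: 1 − s(1 − q). With q = 0.5 (assumed): 95%, 90%, 85% and 75%.

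**Day numbering.** Day k is k − 1 days after Day 1. Day 3-5 is therefore 2 to 4 days after Day 1, Day 15 is 14 days and Day 29 is 28 days. These match the stated offsets from onset only if Day 1 is onset. If Day 1 falls L days later, Day 3-5 is L + 2 to L + 4 days after onset and Day 29 (±7) is L + 21 to L + 35. The documents give no L. For illustration: L = 0 gives 2-4 and 21-35; L = 2 gives 4-6 and 23-37; L = 4 gives 6-8 and 25-39.

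**The case against.** Read in sequence, the stop sentence can be taken as the other branch of the Part 2 gate: it would apply when the criteria are no longer met and no swab is known to be positive. The recall clause supports that reading, because it describes women who stopped with results unavailable. Most of Section 8.1.2.1, and footnote e of the schedule, then agree that a positive swab keeps a woman in. This stands, and it makes the likely intention fairly clear. It does not remove the conflict. Footnote c asks for the criteria on both days with no swab route, the stop sentence carries no exception, and sites often work from the schedule.

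A reader might go further and infer that every PCR-positive woman with a short illness loses her early sample, or that the viral-load data come mainly from women who are still ill. The documents do not support either. Women with an outside positive PCR still meet the criteria, the first two swabs precede the gate, and the recall clause restores the weekly swabs for those who stopped with results pending.

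A reader might also infer that samples after an outside test are late by a definite number of days. No lag from onset to awareness is given, surveillance prompts run at least twice a week, and Section 8 requires actual sample dates and times to be recorded. Time since onset can therefore largely be recovered in analysis.

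**Conclusion.** The contradiction is real but narrow. It concerns women positive on a study swab, without an outside positive PCR, whose symptoms have resolved by a visit held 2 to 4 days after onset. The loss is conditional on a site applying footnote c or the stop sentence. It then consists of the early serum and PAXgene sample and, without recall, the weekly swabs. Day 29 blood goes only under a literal reading of the stop sentence. The exploratory post-infection immune-response and severity-biomarker data would be partly selected on symptom duration, to an extent that depends on s and cannot be derived from the protocol.

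The Day 1 anchors are inconsistent as well, with a smaller consequence. Only exploratory endpoints are touched. Severity: minor.

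**What to change.** Reword footnote c of Section 1.3.4 and the stop sentence in Section 8.1.2.1 so that both carry the gate already written for Part 2: criteria still met on Day 3-5, or at least one positive Day 1-2 or Day 3-5 swab.

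Reconcile the Day 1 anchors between Section 1.3.4 (footnotes b and f) and Section 8.1.2.1, so that each route of entry has one reference date. This should cover Day 15 and Day 29 for a woman who has no symptom onset.

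The cost is a few lines of text and no new procedure. One gap remains: a recovered woman whose results are pending at the visit still misses the early blood. Closing it would need an added draw, which is a trade-off against the stated aim of Amendment 7 to reduce participant burden. It is not part of this correction.
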